Therapists will be consented during a study meeting at each agency where we will provide lunch and information about the study. At that meeting, the manager of research projects, with the assistance of the biostatistician, [name], will randomize therapists into one of the three measurement arms. To maintain balance, we will ensure that we have equal numbers of therapists in each study arm in each site.

Therapists report approximately 30 client encounters per week. We base our projections for youth clients on administrative data from Medicaid claims. On average, youth attend 5.7 sessions (SD = 8.6). Our recruitment goal is 3 unique encounters (i.e., separate clients who each had a CBT session) per therapist for a total of 405 youth client encounters. We will use sequential sampling to identify client encounters to include in the trial. We will sample as a function of individual client session number to ensure that we enroll clients receiving services across the treatment span because CBT techniques used in sessions early on in treatment are different than those used later in treatment. For example, treatment of anxious youth would typically begin with psychoeducation and rapport building in initial sessions before progressing to exposure strategies later in treatment. Once therapists are enrolled in the study, our research staff will work with the therapists directly each week to provide the information they need to check in with eligible families for participation (e.g., recruitment notice, script to obtain verbal assent/consent for the research team to approach the family). Because of our desire to randomly sample treatment sessions from different treatment stages (2-9 (early treatment) and 10+ (late treatment)), we will first randomly select the days the research staff will be present at the agency and then randomly select the blocks of time within each day (per each therapist’s schedule) during which the research staff will enroll clients for each therapist. For instance, if we randomly select Monday, Tuesday and Wednesday as the days the

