Aim 3: Up to 170 therapists and 12 individuals in leadership positions (i.e., supervisors and administrators) will be recruited to participate in a brief quantitative survey during data collection in Aim 1 that will address Aim 3 objectives. For the qualitative data collection, we will use purposive sampling to recruit 48 individuals. The sample will include 36 therapists (12 therapists from each of the three conditions) and 12 individuals in leadership positions (supervisors and administrators). We selected 12 for each group of interest given research that suggests this is the ideal number for thematic saturation.

Motivation will be quantitatively measured using a 7-point scale. This item will be compared for each of the three methods. We will ask therapists about their current and future motivation to use their assigned fidelity method. Because of concerns that willingness to adopt could be influenced by social interaction between therapists in various conditions, we will measure knowledge of the other conditions in the willingness to adopt measure as a potential covariate to be included in the mixed-effects multivariate regression models for Aim 3.

Qualitative data will be collected using validated, standard open-ended questions that have been developed to elicit the beliefs underlying one's motivation. For example, we will ask advantages and disadvantages the stakeholders attribute to using the particular method they were assigned to, as well as direct observation. We will also ask who they believe will approve and disapprove of them using a particular method. These and other questions will be asked to identify perceived barriers and facilitators influencing use of that method. We will also ask therapists and leadership to elaborate upon the quantitative scores provided on the willingness measure, and to generate information on their beliefs about the integration of these techniques in supervision in the future. All of the questions will be compiled in a questionnaire that will undergo cognitive response testing, which is a strategy that identifies ambiguous or awkward wording. Once the participant completes the qualitative interview (est. time, 1 hour), they have completed participation for this study.

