All research activities for Aims 1 and 3, including data collection and engagement with human subjects, will be conducted by members of the University of Pennsylvania research team. All Aim 2 research activities will be conducted by members of the University of Pennsylvania research team as well as by co-investigators from Temple University.

ANALYSIS PLAN

All analyses are by intent-to-treat and will occur at the University of Pennsylvania Center for Mental Health Policy and Services Research under the direction of study biostatistician, [name]. Differences across the three arms of the study will be analyzed using SAS PROC MIXED. We will conduct three mixed-effects multivariate regression models. The dependent variable is difference in score between direct observation and the specific fidelity method under consideration. We will measure the dependent variables in three ways: raw score adherence, raw score competence, and total fidelity t-score (composite of adherence and competence raw score). We will conduct two sets of analyses. In the first set, the model will include two fixed effects (fidelity measurement method and site) and a random effect for therapist to account for the nesting

of patients within therapists. Our primary interest is in the beta coefficient for the fidelity measurement method, which tells us whether there is any difference in accuracy between the intervention arms. Our first hypothesis is that both chart-stimulated recall and behavioral rehearsal (i.e., total fidelity t-score) will be more accurate than self-report. Our second hypothesis is that chart-stimulated recall will capture adherence best. Our third hypothesis is that behavioral rehearsal will capture competence best. To test these hypotheses, we will use the model described above to conduct custom contrasts in the regression models to examine whether the mean of the dependent variable differs for each pair-wise comparison of our intervention arms. We will then repeat that analysis after transforming the dependent variable into t-scores to allow computation of standardized differences for each pairwise comparison, so that we can rank accuracy. The second model will include an additional fixed-effect term for time and an interaction (time X fidelity measurement method), allowing us to examine if there are changes in outcome over time by measurement method. This is important in case there are differential practice effects across condition over time.

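### Aim 3 leaves open adjusting the motivation comparison for knowledge of the other arms, a variable measured after randomisation that can move the contrast away from the effect of assignment

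*Combined protocol and SAP*

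**What the plan says.** All references are to the combined protocol and SAP.

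- **Outcome** (PROCEDURES, Aim 3). "Motivation will be quantitatively measured using a 7-point scale. This item will be compared for each of the three methods". The question concerns the therapist's own arm: "We will ask therapists about their current and future motivation to use their assigned fidelity method".
- **Covariate** (same section). The stated worry is that "willingness to adopt could be influenced by social interaction between therapists in various conditions". The response is to measure knowledge of the other arms within the willingness-to-adopt measure, "as a potential covariate to be included in the mixed-effects multivariate regression models for Aim 3".
- **Timing.** Therapists and agency leaders complete a "brief quantitative survey during data collection in Aim 1 that will address Aim 3 objectives". Randomisation comes earlier: under PROCEDURES, Aim 1, the study team "will randomize therapists into one of the three measurement arms" at the meeting where therapists give consent, with equal numbers per arm within each site.
- **Analysis** (ANALYSIS PLAN). The only general principle is "All analyses are by intent-to-treat". The models written out there are the Aim 1 accuracy models: method and site as fixed effects and therapist as a random effect, then time and its interaction with method. There is no Aim 3 model, no rule for when the knowledge variable enters, and no statement that the contrast without it is the main one.

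**The concern.** Objective 3 compares motivation across randomised methods. Randomisation protects that comparison as long as the model conditions only on things that assignment cannot change. Knowledge of the other arms is not such a variable by construction. It is recorded after assignment, and the reason for recording it is contact between therapists who are already in different arms. It may also reflect traits, such as engagement, that influence motivation.

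If assignment changes the knowledge and the knowledge goes with motivation, the adjusted arm coefficient no longer estimates the effect of being assigned a method. It also need not estimate the effect that would have been seen without contamination, because the shared trait is not in the model. Calling the covariate only potential leaves the choice between the two contrasts open until the data have been seen.

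**Working it through.** **Is the variable post-randomisation?** The text does not use the term, so this is an inference from three facts: the survey runs during Aim 1 data collection while randomisation takes place at the consent meeting; the outcome refers to the assigned method; and the rationale is interaction between therapists in different conditions. That the knowledge item and the motivation rating share one instrument is read from the Aim 3 text, which places the item in the willingness measure and uses willingness and motivation for the same construct.

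**What adjustment does.** Let A be arm (two arms, 0/1), K knowledge and Y motivation, with K and Y scaled to a within-arm SD of 1. Let a be the mean difference in K between arms, b the within-arm slope of Y on K, and τ the effect of assignment on Y. In the linear model with A and K, the coefficient of A is

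τ − a × b.

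The shift from τ is therefore −a × b. It vanishes if either a or b is zero. If one unmeasured trait correlates ρ with both K and Y, then b = ρ², and the shift in absolute value is a × ρ².

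**Inputs.** The documents give no value for a, b or ρ, and no SD, effect size, alpha or power for Aim 3, so there is no stated figure to reproduce. The values of a and ρ below are assumptions. Arm size comes from the documents in two ways: about 56 per arm (Executive Summary), or 405 clients ÷ 3 per therapist = 135 therapists, ÷ 3 arms = 45 per arm.

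**Size of shift, a × ρ², in SD units:**

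| a | ρ = 0.3 | ρ = 0.5 | ρ = 0.7 |
|---|---|---|---|
| 0 | 0 | 0 | 0 |
| 0.2 | 0.018 | 0.050 | 0.098 |
| 0.5 | 0.045 | 0.125 | 0.245 |
| 0.8 | 0.072 | 0.200 | 0.392 |

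**Against sampling error.** The standard error of a simple arm difference is √(2/n): √(2/56) = 0.19 and √(2/45) = 0.21. For a = 0.5 the shift runs from 0.045/0.19 = 0.2 to 0.245/0.19 = 1.3 standard errors with 56 per arm, and from 0.045/0.21 = 0.2 to 0.245/0.21 = 1.2 with 45.

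**Simulation check.** Two arms of 56, normal data, one shared trait, no true arm effect, two-sided 5% test, 10,000 runs per setting. Here r is the within-arm correlation of K with Y, so r = ρ².

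| a | r | mean shift (SD) | false-positive rate, adjusted |
|---|---|---|---|
| 0 | 0.3 | 0.00 | 5.1% |
| 0.5 | 0.3 | −0.15 | 12.6% |
| 0.5 | 0.5 | −0.25 | 30.6% |
| 0.8 | 0.5 | −0.40 | 61.2% |

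The shifts match −a × r. The contrast without K rejected in 4.6% to 5.2% of runs in the same settings. The simulation omits site and repeated ratings; it illustrates the mechanism and does not forecast this trial.

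**The case against.** The strongest reply is that nothing in the documents shows an arm difference in knowledge, and parts of the design favour balance. Therapists at an agency hear about the study at a common meeting, so some knowledge of all arms may precede randomisation. Equal arm sizes within each site should make contact with colleagues in other arms similar. If a = 0, adjustment does no harm and may gain a little precision: the standard error is multiplied by √(1 − r²), which at r = 0.49 is √(1 − 0.24) = 0.87. The item addresses a real risk in a design that mixes arms within sites, and the text commits to nothing beyond a potential covariate.

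Much of this stands. An arm difference is possible, not shown, and measuring the item is sensible. But the sponsor cannot know beforehand that a is zero. Burden and staff contact differ by arm: self-report is completed on the therapist's own time after brief training, while the other two arms meet research staff for about an hour. The protocol's own worry, that interaction could influence willingness, also supposes that b is not zero.

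Three stronger readings are tempting and not supported:

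- *The adjusted contrast is biased.* That needs both a and b to be non-zero, and the documents establish neither.
- *Adjustment breaks the intent-to-treat promise.* Every therapist would still be analysed in the assigned arm. What changes is the quantity estimated.
- *One common slope has no meaning because the other conditions differ by arm.* That depends on the wording and scoring of an instrument that the documents do not contain. An overall familiarity score could share a scale across arms.

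**Conclusion.** The point holds as a conditional one. The plan keeps open an adjustment for a variable measured after assignment and alongside the outcome, and nowhere makes the contrast without it primary. If assignment affects that variable and it is related to motivation within arm, the adjusted contrast departs from the effect of assignment.

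Direction and size in this trial cannot be computed. The shift is nil with no arm difference in knowledge, and about 0.05 to 0.25 SD in absolute value under the assumed 0.5 SD difference with a shared-trait correlation of 0.3 to 0.7, or roughly 0.2 to 1.3 standard errors. A smaller assumed difference of 0.2 SD gives 0.02 to 0.10 SD.

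A reader might infer that the accuracy results are affected too. They are not: the Aim 1 models do not list this covariate. The change is worth making because it is nearly free and settles the choice before the data are seen.

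**What to change.** Add to the ANALYSIS PLAN that the main Aim 3 comparison of motivation, among randomised therapists, has arm and site as fixed effects, keeps the mixed-effects structure already planned, and excludes knowledge of the other conditions. Agency leaders, who are not randomised, stay outside this contrast.

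Keep collecting the knowledge item. Summarise it by arm as a description of contamination. Label any model that adjusts for it as sensitivity or exploratory, and note there that it need not recover the contamination-free effect.

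The cost is two or three sentences of text, with no new data, no change to the questionnaire and no loss of sample.

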Therapist fidelity is frequently measured due to its mediating role between implementation of evidence-based practices and client outcomes. Fidelity can also be conceptualized as an indicator of quality of care, which is a priority for many national organizations such as the Institute of Medicine. Fidelity includes adherence (how closely the components of a protocol are followed) and competence (how skillfully the components are implemented and therapist responsiveness to the child). The gold-standard fidelity measurement technique is direct observation, which is infeasible in community agencies due to lack of recording devices, time, and trained coders. Community mental health clinics sorely need methods of measuring fidelity that are accurate and cost-effective. Accurate methods refer to those with strong reliability and validity, whereas cost-effective methods refer to those that can be used with the limited resources in routine practice settings while providing benefit.

Therapists' self-report of their own fidelity is easy to administer, brief, and low-cost. However, the correspondence between self-report and independent observers is low (e.g., kappa of .22 in one

study). Leading scholars have suggested that self-report is frequently inaccurate because self-report measures typically include many terms that are unfamiliar to therapists; and because therapists are not trained in rating their own behavior (i.e., how to rate high vs. low behavior). One way to address these concerns is to ensure that the operational definitions of each item are clear and to train therapists in how to rate their own behavior. Additionally, two innovative methods from the medical literature, chart-stimulated recall and behavioral rehearsal, hold promise for fidelity measurement. Chart-stimulated recall entails a brief interview with a clinician about the care provided to a client, while allowing the clinician to review the client's file to assist recall. Behavioral rehearsal refers to a simulated interaction between a clinician and another individual around treatment delivery. Our goal is to test the accuracy, costs, and cost-effectiveness of each of these three methods in comparison to direct observation.

STUDY SAMPLE AND DATA SOURCE

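### The accuracy outcome is an unqualified difference from direct observation; read as a signed difference, the arm contrasts and the ranking measure net bias, not accuracy

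*Combined protocol and SAP*

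**What the plan says.** The outcome is defined once, in the Analysis Plan (Executive Summary, item 1): "The dependent variable is difference in score between direct observation and the specific fidelity method under consideration". It is formed on three scales: adherence raw score, competence raw score and a total fidelity t-score.

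The mixed model has fixed effects for method and site and a random effect for therapist. Interest lies in the method coefficient, "which tells us whether there is any difference in accuracy between the intervention arms". The hypotheses are tested by custom contrasts "to examine whether the mean of the dependent variable differs for each pair-wise comparison of our intervention arms". The dependent variable is then converted to t-scores to give "standardized differences for each pairwise comparison, so that we can rank accuracy".

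The Background says what accuracy is meant to be: "Accurate methods refer to those with strong reliability and validity". It describes the weakness of self-report as one of agreement: "the correspondence between self-report and independent observers is low (e.g., kappa of .22 in one" study).

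No section gives the order of subtraction, an absolute or squared difference, a rule for ranking by distance from zero, or an agreement statistic for comparing arms.

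**The concern.** The mean of a signed difference is net bias. A method that over-rates half its sessions and under-rates the other half by the same amount has a mean of zero, however large the errors. A contrast of two such means therefore does not show which method is closer to direct observation. It can fail in three ways:

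- it misses a real difference in accuracy when methods differ in spread and not in bias;
- it reports a difference when two equally accurate methods err in opposite directions;
- it puts a noisy method with little net bias ahead of a more precise one with some bias.

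This variable carries Objective 1 and all three hypotheses. If an absolute difference was meant, the form of the main outcome is still open, and the two forms can lead to opposite conclusions from the same data.

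**Working it through.** **Inputs from the protocol.** The target is 3 encounters "per therapist for a total of 405 youth client encounters" (Procedures, Aim 1). This gives 405/3 = 135 therapists and 135/3 = 45 per arm. The Executive Summary gives about 56 per arm. The protocol states no power, alpha, effect size, SD or ICC for this comparison, so there is no design figure to reproduce.

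**Assumptions.** Errors D are normal with bias *m* and SD *s* in arbitrary units. There are 3 sessions per therapist, the therapist ICC ρ is 0.1 or 0.5, and alpha is two-sided 0.05. Two arms are compared on therapist means by an unequal-variance t-test, without the site effect, in 4,000 replicates per setting.

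**Formulas.**

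- Signed: E(D) = m, so the contrast estimates m₁ − m₂ and *s* drops out.
- Mean absolute error (MAE): E|D| = s√(2/π)·exp(−m²/2s²) + m[1 − 2Φ(−m/s)].
- Mean squared error: E(D²) = m² + s².
- Standard error of the signed contrast with n therapists per arm: √[(s₁² + s₂²)(1 + 2ρ)/(3n)].

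**Two cases by hand, n = 45, ρ = 0.5.**

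- Bias +0.4 v −0.4, SD 1. MAE = 0.798·exp(−0.08) + 0.4·(1 − 2·0.345) = 0.86 in both arms. SE = √(2·2/135) = 0.172 and 0.8/0.172 = 4.65, so rejection is about Φ(4.65 − 1.96), over 99%, although accuracy is equal.
- Bias 0, SD 2 v bias 0.5, SD 1. SE = √(5·2/135) = 0.272 and 0.5/0.272 = 1.84, so rejection is about Φ(−0.12) = 45%. The arm with mean zero is the less accurate one (MAE 1.60 v 0.90).

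**Simulation.** Ranges cover both sample sizes and both ICCs.

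| Case | Bias/SD, arm 1 v arm 2 | MAE | Signed rejects | Absolute rejects |
|---|---|---|---|---|
| a | 0/2 v 0/1 | 1.60 v 0.80 | about 5% | 100% |
| a, milder | 0/1.25 v 0/1 | 1.00 v 0.80 | about 5% | 50–74% |
| b | +0.4/1 v −0.4/1 | 0.86 v 0.86 | over 99% | 5–6% |
| c | 0/2 v 0.5/1 | 1.60 v 0.90 | 44–74% | not needed for the point |
| d | 0.5/2 v 1.0/1 | 1.65 v 1.17 | 45–76% | 85–98%, right arm |
| e | 3.0/1 v 2.5/1 | 3.00 v 2.50 | 82–99% | 82–99% |
| f | 1.0/1 v 0.5/1 | 1.17 v 0.90 | 82–98% | 62–88% |
| f, smaller bias | 0.5/1 v 0/1 | 0.90 v 0.80 | 82–99% | 17–27% |

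In case c the less accurate arm has the mean nearer zero in roughly 93% to over 99% of the significant results. In case d, where both biases share a direction, this happens every time.

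**The t-score step.** A t-score is a linear rescaling, so it keeps sign and cancellation. With biases of +0.5 and −0.5 and SD 1, equally accurate arms become about 55 and 45.

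**The case against.** The strongest reply is that the text leaves the term undefined and does not choose a wrong outcome. No order of subtraction is given, and the talk of capturing adherence or competence best and of ranking accuracy fits distance from direct observation better than signed bias. If the analysts meant the absolute difference, one sentence removes the harm. That is fair, but the sentence is absent, and an analyst following the plan as written could fit the signed difference.

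Second, the damaging cases are assumed. Case b needs opposite biases; cases c and d need the noisier method to be the less biased one, with a 2:1 SD ratio. The protocol supports neither. If the worse method is both noisier and more biased in the same direction (1.5/1.25 v 1.0/1), the signed contrast is significant in 71–96% with the better arm nearer zero in essentially all of those; the absolute difference gives 86–99%. This stands, and it limits how often harm should be expected. It does not touch case a, which needs only unequal spread. Self-rating, interview and role-play are different enough that equal spread should not be presumed.

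Third, the absolute difference costs power when spreads are equal and small biases share a direction (case f). This also stands. Bias is part of accuracy, so the signed mean is incomplete and not irrelevant, and it should still be reported.

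Last, mean absolute error is not chance-corrected agreement either, so it does not by itself answer the kappa argument in the Background. That is why an agreement measure belongs beside it.

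**Conclusion.** The concern holds. As written, the plan contrasts and ranks arm means of an unqualified difference; on the signed reading it tests net bias and not accuracy in the protocol's own sense of reliability and validity. The possible consequences run from about 5% power against a twofold accuracy gap, through over 99% rejection when accuracy is equal, to ranking the less accurate method first. These sizes rest on assumed biases, SDs and ICCs; the size in this trial is unknown. The signed contrast is safe if all methods err in the same direction in nearly every session, and it also orders methods correctly when biases share a direction and spreads are similar. The protocol neither states nor justifies either condition. Because the variable serves Objective 1 and every hypothesis, it must be settled before analysis.

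**What to change.** Define the dependent variable for the Objective 1 contrasts and ranking as the per-session absolute (or squared) difference from direct observation, for adherence, competence and total fidelity, with smaller values meaning more accurate. If t-scores are used for ranking, take the absolute or squared difference first.

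Report by arm, as secondary results, the mean signed difference with its direction defined, and an agreement measure such as limits of agreement or the ICC with direct observation. Use robust standard errors or arm-specific variances, since absolute differences are skewed and their spread is likely to differ by arm.

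The cost is plan wording and a few lines of SAS; no new data or design change is needed. The price is lower power where methods differ only by a small bias in a shared direction with equal spread, and the reported signed difference covers that situation.

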research staff will be at the agency that week and a therapist participant planned to be at the agency from 11 AM to 7 PM each of those days, then we would randomly select either the first block (11 AM to 3 PM) or the second block (3 PM to 7 PM) of time in which to approach clients of that therapist. Before each block of time begins, the research staff will check in with the therapist to determine how many of the clients scheduled for that block of time are eligible (i.e. youth clients 7-24 years with whom the therapist uses CBT strategies). We will also ask the therapist to indicate if the client is in early or late treatment stages. We will ask therapists to introduce the study to eligible clients within each randomly selected block of time until three clients have been enrolled. We will provide \$25 compensation to complete this process until 3 separate clients who each had a CBT session are enrolled (we will not include if the therapist identifies the session as a crisis of the week session). Based on conversations with our community advisory board, we have been advised that we will need to be flexible at each agency with regard to how we ascertain this information.

We will not have research staff directly approach families to avoid confidentiality concerns. Therapists will approach the family and obtain verbal consent and assent for the research team to contact the family. Any randomly selected child aged 7-24 who is presenting for treatment for any psychosocial difficulties may participate. Exclusion criteria include if the child does not have a legal guardian who can consent to their participation (e.g., DHS-involved youth). Children and their families will be recruited and retained with the help of study team members who will be embedded within agencies where enrolled therapists are seeing eligible clients. When study team members learn of a consent to contact from the therapist, they obtain verbal or written consent and assent from the guardian and client to record the encounter. If the therapist and client both request that a research team member sit with the recorders during the session, then a research team member will sit in the room and hold the recorder. Youth will be paid \$10 for allowing their therapy session to be audio-taped. Study participation for youth only entails recording their one session.

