Due to COVID-19, we have also decided to implement remote recruitment of therapists and clients. Research staff will recruit therapists by emailing them directly and introducing the study. If therapists are interested in participating in the study, research staff will consent therapists over the phone. Once consented, research staff will work with therapists to identify eligible clients using sequential sampling, which will ensure that we enroll clients receiving services across the treatment span. Therapists will introduce the study to eligible clients (and if necessary, guardians) via a virtual platform to obtain verbal consent (and if necessary, assent). If the client (and if necessary, guardian) are interested, research staff will enroll and consent clients through a virtual platform. Research staff will place the audio recorder next to the computer in a private room, press “record” on the audio recorder, close the door and leave the room. Therapists will notify the research staff through text message once the session is over. Youth will be paid with an electronic \$10 Amazon gift card for allowing their therapy session to be audio-taped.

All three conditions (described below) will be compared with direct observation (i.e., audio-recordings of each session). Therapists will be randomized to one of the three experimental measurement conditions. Therapists in the self-report condition will be asked to complete the self-report measure within 48 hours of the encounter, to ensure appropriate recall and also because that is typically when therapists are expected to complete their notes (personal communication, [name], Community Behavioral Health). Therapists in the other two conditions will

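### Should treatment stage, which guides how sessions are sampled, also be a term in the Aim 1 analysis models?

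*Combined protocol and SAP*

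**What the plan says.** PROCEDURES, Aim 1, explains the sampling: "We will sample as a function of individual client session number to ensure that we enroll clients receiving services across the treatment span". The reason given is that "CBT techniques used in sessions early on in treatment are different than those used later in treatment". Two stages are defined by session number, "2-9 (early treatment) and 10+ (late treatment". No number of sessions per stage is fixed; enrolment runs through randomly chosen time blocks until a therapist has three clients.

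Stage comes from the therapist: "We will also ask the therapist to indicate if the client is in early or late treatment stages". The same section adds, on agency advice, that "we will need to be flexible at each agency with regard to how we ascertain this information". For remote recruitment, staff work with therapists to "identify eligible clients using sequential sampling, which will ensure that we enroll clients receiving services across the treatment span".

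Allocation comes earlier. At the study meeting the team "will randomize therapists into one of the three measurement arms", with equal numbers per arm within each site.

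The ANALYSIS PLAN defines the outcome as the direct-observation score minus the score from the assigned method. In the first set of models, "the model will include two fixed effects (fidelity measurement method and site) and a random effect for therapist". The second set adds time and its interaction with method, to look for practice effects that differ by condition. Stage is in neither set.

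**The concern.** When a protocol builds a factor into its design and explains why that factor matters, one expects to find it in the model. Here the protocol says that early and late sessions differ in content, samples with that in mind and asks therapists for the stage, yet the models ignore it. The time term does not clearly fill the gap, since its stated purpose points to the order of a therapist's encounters and not to the client's session number.

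Two things could be at stake. If the difference score varies with stage, omitting stage leaves explainable variation in the error and costs precision. If stage mix differed systematically between arms, the method contrasts would be biased. The second is conceivable because clients are chosen after therapists have been randomised.

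**Working it through.** **1. Does the design require the term?** The factor balanced at randomisation is site, and site is a fixed effect. Stage is not a randomisation factor; it is used so that the sampled sessions cover the course of treatment. Omitting it leaves analysis and allocation matched. The unadjusted contrast estimates the difference in accuracy averaged over the sampled mix of sessions, which is the quantity this sampling is meant to deliver.

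**2. Does a stage effect on technique imply one on the outcome?** Let stage shift the observed score by s and the method's score by s′. The outcome is their difference, so its stage effect is b = s − s′. If both scores move together, b = 0 however much technique changes. The protocol states that technique differs by stage; it does not state that the discrepancy between two ratings of one session does.

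**3. How much precision could be lost?** The documents give no stage effect, intraclass correlation (ICC) or realised stage mix, so these are assumptions.

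- From the documents: 3 clients per therapist; 405 encounters, hence 405/3 = 135 therapists and 45 per arm; up to 170 therapists, hence about 56 per arm; sessions attended, mean 5.7, SD 8.6.
- Late share p if sampling is blind to stage: E[(N−9)+]/E[(N−1)+], fitted to that mean and SD, gives 0.34 (lognormal) to 0.42 (negative binomial).
- Assumed: b from 0 to 0.8 within-therapist SD.

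With within-therapist SD = 1, let vb = ICC/(1−ICC), and let vS be the variance of a therapist's mean stage over three sessions. Then

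reduction in SE = 1 − √[(vb + 1/3)/(vb + 1/3 + b²·vS)].

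For stage-blind sampling, vS = p(1−p)/3 = 0.42 × 0.58/3 = 0.0812. If every therapist contributes both stages, with one or two late sessions equally likely, vS = 0.25/9 = 0.0278.

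| Sampling | b | ICC | b²·vS | vb + 1/3 | SE reduction |
|---|---|---|---|---|---|
| Stage-blind | 0.3 | 0.2 | 0.0073 | 0.5833 | 0.6% |
| Stage-blind | 0.8 | 0.5 | 0.0520 | 1.3333 | 1.9% |
| Stage-blind | 0.8 | 0.2 | 0.0520 | 0.5833 | 4.2% |
| Stage-blind | 0.8 | 0 | 0.0520 | 0.3333 | 7.0% |
| Both stages | 0.3 | 0.2 | 0.0025 | 0.5833 | 0.2% |
| Both stages | 0.8 | 0.2 | 0.0178 | 0.5833 | 1.5% |

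At b = 0 the reduction is zero.

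A second parameterisation agrees. If stage explains a share R² of total variance, the SE ratio is √{[ICC + (1−ICC−R²)/3]/[ICC + (1−ICC)/3]}. For R² = 0.05 this gives √0.95 = 0.975 at ICC 0 and √(0.650/0.667) = 0.987 at ICC 0.5, a reduction of 1.3% to 2.5%.

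In simulation (45 therapists per arm, power near 80%, 6,000 paired runs, Monte Carlo SE 0.1 to 0.35 points), adjustment changed power by −0.2 to +0.6 points at b = 0.3 and by −0.3 to +0.1 points at b = 0.

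**4. Does chance imbalance matter?** The 95% range of the difference in late share between two arms is ±1.96·√(2·vS/n). With stage-blind sampling, p = 0.42 and n = 45, this is 1.96 × √(2 × 0.0812/45) = 0.118, about 12 points. It needs no correction: b²·vS is part of the variance between therapist means, from which the unadjusted standard error is estimated.

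**The case for a change.** The strongest opposing case is about selection, not precision. Clients are enrolled after randomisation, and therapists judge who is eligible, report the stage and label crisis sessions, which are then replaced. Random time blocks limit this in person, but the remote procedure mentions only sequential sampling. If stage mix drifted by arm, the unadjusted contrast would be biased. Take half the sessions as late and R² = 0.05, so b = √0.05/0.5 = 0.447 total SD. A 10-point difference in late share then shifts the contrast by 0.045 SD. With SE = √{2[ICC + (1−ICC)/3]/n}, n of 45 to 56 and ICC 0.1 to 0.3, that is 0.29 to 0.37 SE, and a nominal 5% test runs at about 6.0% to 6.6%.

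The arithmetic stands, but its premise does not: nothing in the documents shows or implies that stage mix differs by arm. The same mechanism also weakens the remedy. A stage report collected after allocation, through a therapist already assigned to an arm, is not a baseline covariate and could itself depend on arm. It may also be incomplete, given the flexibility by agency. A main effect would correct only for stage, not for other consequences of selection, and would not show whether a method's accuracy changes with stage.

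It is also true that the term is cheap if stage has no effect, and that a table of stage by arm would be informative. Such a table adds description and changes no result. The gap at session 1 is minor, since the stated sampling range starts at session 2.

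**Conclusion.** The concern does not hold. Stage does guide sampling and is absent from both models, but the plan is not wrong for that. The randomisation factor is in the model, the same-session difference removes any stage shift common to both scores, and the contrasts are valid provided stage mix is unrelated to arm, which the documents give no reason to doubt.

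The possible gain from adjustment is unestablished. It is nil if stage does not affect the difference score, about 0.6% in standard error at 0.3 SD (ICC 0.2, stage-blind, 42% late), and 1.9% to 7.0% at the assumed extreme of 0.8 SD as the ICC falls from 0.5 to 0. If stage also clustered within therapist with correlation 0.3, vS would be 0.0812 × 1.6 = 0.130, and the reduction at 0.8 SD would be 6.4% at ICC 0.2 and 10.5% at ICC 0. These figures rest on assumed effects and correlations, so they illustrate the range and are not a firm ceiling. Given that stage is ascertained after allocation, whether to adjust for it is a choice on which competent statisticians would differ.
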